agents. In mCRPC patients facing advanced illness with little hope for a cure, the focus of treatment shifts from active anti-cancer treatment to palliative care for relief of physical symptoms, maintaining function, and attempting to improve their health-related quality of life (Cella et al 2009). Therefore, in addition to tracking essential clinical outcomes, it is also important to assess and evaluate changes in HRQoL of such fragile patients as they receive treatment.

Several agents have been approved for the treatment of mCRPC, and NCCN, ASCO, ESMO, and APCCC guidelines provide some consensus and guidance for their use. Regardless, none of these therapies are proven to prolong survival after enzalutamide or abiraterone. In practice, abiraterone acetate or enzalutamide are often used in the first-line mCRPC setting; Sipuleucel-T is best used in mildly asymptomatic small volume disease; and ²²³Radium is used to treat men with bone-only disease. Taxane-based chemotherapy is most often used today after abiraterone or enzalutamide and for symptomatic patients, particularly with visceral disease. Docetaxel is used more commonly than cabazitaxel. Because both agents have a typical chemotherapy side effect profile, they are often not considered for patients due to comorbidity, poor hematological reserve, or patient refusal (Zielinski et al 2014).

Six small published series with a total of 499 patients have examined the efficacy of either abiraterone or enzalutamide in men previously exposed to a taxane and either abiraterone or enzalutamide. These modern hormonal agents produced only modest activity, including PSA decline >50% in 4% to 22% of patients, a median PFS of 2.7 to 4.6 months and a median OS of 7.2 to 12.2 months (Azad et al 2015, Cheng et al 2015, Badrising et al 2014, Brasso et al 2015, Loriot et al 2013, Noonan et al 2013). It's important to note that this is in contrast with the level of anti-tumor activity demonstrated in the pivotal clinical trials for these agents that led to approval. In that setting, patients had only received prior docetaxel and had not been exposed to prior therapy with either abiraterone or enzalutamide. As these modern hormonal agents have been used in earlier lines of therapy, the use of a second agent following docetaxel has resulted in diminished efficacy, likely due to cross resistance.

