Of the screened patients, 70% were identified as PSMA-positive via PET imaging and eligible for treatment. Most subjects had been exposed to at least 1 taxane chemotherapy and either abiraterone or enzalutamide in the mCRPC setting. In this heavily pre-treated patient population with few therapeutic alternatives, 64% of patients on ^{177}Lu -PSMA-617 showed a PSA response defined by a reduction in PSA of at least 50%, and 44% had a reduction of PSA of 80% or more. In 27 patients with measurable disease, the objective response rate in measurable disease as defined by Response Evaluation Criteria in Solid Tumors (RECIST) criteria was 56% (complete response [CR] and partial response [PR]). Median overall survival was 13.3 months (95% confidence interval [CI] 10.5–18.0). Therapy with ^{177}Lu -PSMA-617 was well tolerated. These safety and efficacy data also translated into significantly improved quality of life scores and reduction in pain scores.

In summary, over 40 compassionate use publications and prospective Phase 2 clinical trial data describe the use of ^{177}Lu -PSMA-617 in patients who have been exposed to approved agents. In the post-taxane, post-androgen axis inhibitor setting ^{177}Lu -PSMA-617 has demonstrated a well-established, predictable, well tolerated safety profile. Clinical series indicate the most common adverse effects, predominately Grade 1–2, of ^{177}Lu -PSMA-617 treatment are dry mouth, nausea, vomiting, diarrhea, constipation, fatigue, anemia, thrombocytopenia and neutropenia. The incidence of Grade 3/4 toxicity in the series was very low, and mainly restricted to reversible hematological events. Efficacy has been demonstrated on multiple clinically significant endpoints, including PSA response, soft tissue lesion response measured by RECIST, PFS, OS, pain and quality of life. No standard dose and schedule have been developed.

The preliminary clinical evidence indicates ¹⁷⁷Lu-PSMA-617 may demonstrate clinical benefit in patients with mCRPC in a setting where patients had been exposed to chemotherapy and NAADs and there is no recommended standard of care.

This Phase 3 study will assess the efficacy of ¹⁷⁷Lu-PSMA-617 in patients with progressive PSMA-positive mCRPC by measuring overall survival and rPFS in a randomized, prospective, open-label trial.

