4.2 Sub-study Analyses

The analyses of dosimetry, PK and ECG from the sub-study are described in separate analysis plans and are outside the scope of this SAP. All other analyses as described in this SAP will be performed, at the earliest, when all patients have completed study treatment (i.e. ^{177}Lu -PSMA-617+BSC/BSoc) or discontinued study treatment for any reason. Separate TFL shells will detail the planned outputs for the sub-study analyses.

5. General Analysis Definitions

Data will be analyzed using SAS version 9.4 or higher.

No tests of significance will be carried out to compare treatment arms on baseline data because any observed differences between them must be attributed to chance.

Descriptive statistics will be presented in tables as follows:

- Categorical data will be summarized in contingency tables presenting frequencies and percentages.
- Continuous data will be summarized using number of non-missing values (n), mean, standard deviation, median, minimum, and maximum values.

Unless otherwise indicated, for frequency tables, patients with missing data will be excluded from the denominator of percentage calculations. All treatment arm comparisons other than the one-sided analyses described for the alternate primary endpoints, rPFS and OS, will be based on two-sided tests.

Tables will be created by treatment arm and for all patients combined as described at the beginning of sections 7, 8, and 9.

Individual patient listings will include all study-related data. The sort order of the listings will be by treatment, patient ID (center number-patient number), and date of assessment (if available).

Randomized treatment throughout this document will refer to ^{177}Lu -PSMA-617+BSC/BSoc and BSC/BSoc alone for analyses pertaining to the main study and will refer to ^{177}Lu -PSMA-617+BSC/BSoc for analyses pertaining to the sub-study.

Best supportive/best standard of care (BSC/BSoC): BSC/BSoC in either arm will be administered as per physician's orders and protocol at the institution and whenever feasible, it should be optimized prior to randomization. Patients will continue to be treated with BSC/BSoC until they require a treatment regimen not allowed on study or have radiographic progressive disease as measured by Prostate Cancer Clinical Trials Working Group 3 (PCWG3) criteria. BSC/BSoC is defined as follows:

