5.6 General Variable Definitions

- Time to withdrew consent from ¹⁷⁷Lu-PSMA-617 (days): (Date of withdrew of consent from ¹⁷⁷Lu-PSMA-617 treatment – date of randomization + 1).
- Time to withdrew consent from BSC/BSoC (days): (Date of withdrew of consent from BSC/BSoC – date of randomization + 1).
- Time to withdrew consent from study (days): (Date of withdrew of consent from study – date of randomization + 1).
- Age (years): year of informed consent - year of birth; calculated within clinical database.

- Time since initial prostate cancer diagnosis (years): (Date of informed consent - Date of initial prostate cancer diagnosis)/(365.25). For incomplete dates, see Section 5.2.
- Weight (kg) = weight (lb) * 0.45359237
- Height (cm) = height (in) * 2.54
- BMI (kg/m²) = weight[kg] / (height[m]²) using weight and height at baseline.
- Best % change (where a decrease over time is desirable) = ((smallest post baseline assessment - baseline)/baseline) x 100
- Last taxane therapy treatment-free interval (months): (randomization date - last taxane therapy end date)/(30.4375). For incomplete dates, the see Section 5.2. Taxanes included are those identified as 'Taxane' per WHO Drug ATC Level 4 (e.g. cabazitaxel, docetaxel or paclitaxel).
- Baseline PSA doubling time (months): PSA doubling time will be calculated as natural log of 2 (0.693) divided by the sum of the fixed slope (common to all patients) and the random slope (specific for the patient) of the random coefficient linear model between the natural log of PSA and time of PSA measurement (Svatek et al., 2006). If the PSA doubling time is less than zero (i.e. stable, nonincreasing, or decreasing PSA levels as defined by a negative slope from the random coefficient linear model), the PSA doubling time is set to 0. PSA is collected at screening visit and for the most recent 2 PSA measurements available prior to screening. Calculations will be performed only for subjects with (1) all 3 PSA values with each value ≥ 0.2 ng/mL and (2) for which the interval between the first and last PSA values are ≥ 8 weeks but ≤ 12 months as stated in PCWG3 guidelines (Scher et al., 2016; Pound et al., 1999).

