7.2 Baseline Disease Characteristics

Descriptive statistics of patient disease characteristics at baseline will be presented for the following variables:

- Time since initial prostate cancer diagnosis (years)
- Initial Histopathological Classification
- Initial Histopathological Grade
- Initial Gleason score
 - Categorical: 2-3,4-7,8-10, unknown
- Stage at Initial Diagnosis
- Total Sum of Target Lesions Diameters per RECIST 1.1
- Baseline Target Lesions (Yes vs. No) and Non-Target Lesions (Yes vs. No)
- Site of disease (lung (yes/no), liver (yes/no), lymph node (yes/no), bone (yes/no), other (yes/no) using target and non-target lesions or bone scan assessments (bone only); sponsor to provide categorization)
- Baseline PSA doubling time (months): continuous and categorical (≤ 6 vs. >6)
- Baseline PSA
- Baseline ALP
- Baseline LDH

Note: The baseline variables 'Total Sum of Target Lesions Diameters', 'Target Lesions and Non-Target Lesions' will be based on the data collected on target/non-target lesion assessment according to RECIST 1.1 according to local investigator assessment and documented in the CRF. 'Site of disease' will be based on the data collected on either the target/non-target lesion assessment (per RECIST 1.1) or the bone scan assessment per local investigator assessment and documented in the CRF.

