8.1.3 Additional Secondary Efficacy Definitions

- Progression-free survival (PFS) (months): (Date of first radiographic progression/clinical progression/PSA progression/death/censor – Date of randomization + 1)/30.4375. PFS is defined as the time (in months) from the date of randomization to the date of first evidence of radiographic, clinical or PSA progression or death due to any cause, whichever occurs first. The dates of radiographic, clinical and PSA progression are defined as follows:
 - Date of radiographic progression: defined in Section 8.1.1.
 - Date of clinical progression: earliest date of assessment for when the investigator indicates clinical progression has occurred.
 - Date of PSA progression: Where a decline from baseline is documented, date that a $\geq 25\%$ increase in PSA and an absolute increase of 2 ng/mL or more from the nadir (from all scheduled and unscheduled visits prior to the current visit being evaluated) is documented and confirmed by a second value obtained 3 or more weeks later. Rises in PSA within the first 12 weeks of date of first dose of randomized treatment will be ignored.
Where no decline from baseline is documented, PSA progression is defined as a $\geq 25\%$ increase from the baseline value along with an increase in absolute value of 2 ng/mL or more after 12 weeks from the date of first dose of randomized treatment (with confirmation obtained 3 or more weeks later) as specified in PCWG3 guidelines.
 - Date of censoring for PFS: Censoring date is the same as defined for rPFS.
- PSA doubling time (months): PSA doubling time will be calculated as natural log of 2 (0.693) divided by the sum of the fixed slope (common to all patients) and the random slope (specific for the patient) of the random coefficient linear model between the natural log of PSA and time of PSA measurement (Svatek et al., 2006). If the PSA doubling time is less than zero (i.e. stable, nonincreasing, or decreasing PSA levels as defined by a negative slope from the random coefficient linear model), the PSA doubling time is set to zero. The calculation will be based on (1) latest baseline PSA measurement ≥ 0.2 ng/mL, (2) at least three consecutive (scheduled and unscheduled) post-baseline PSA values with each value ≥ 0.2 ng/mL, and (3) interval between first and last PSA values of ≥ 8 weeks but ≤ 12 months as stated in PCWG3 guidelines (Scher et al., 2016; Pound et al., 1999).

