If the baseline PSA value prior to first dose of randomized treatment is missing or < 0.2 ng/mL, PSA doubling time will be missing.

For interpretation of PSA doubling time it should be noted that PCWG3 guidelines state the calculation should be based on the most recent PSA values during androgen deprivation therapy. These additional criteria will not be applied.

- PSA response: PSA response is defined as the proportion of patients who have a $\geq 50\%$ decrease in PSA from baseline that is confirmed by a second PSA measurement ≥ 4 weeks later. All scheduled and unscheduled PSA assessments will be used to determine and confirm PSA response.
- PSA $> 80\%$ decrease: PSA $\geq 80\%$ decrease is defined as the proportion of subjects that have a $\geq 80\%$ decrease in PSA from baseline that is confirmed by a second PSA

measurement ≥ 4 weeks later. All scheduled and unscheduled PSA assessments will be used to determine and confirm a PSA $\geq 80\%$ decrease.

- Duration of PSA response (only for patients with response) (months): (date of PSA progression/censor – Date of PSA response + 1)/30.4375. Duration of PSA response is defined as the duration (in months) between the date of first document PSA response (i.e. $\geq 50\%$ decrease in PSA from baseline) and earliest date of PSA progression as defined above. The censoring date is the date of last PSA assessment.

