8.2.3.2 Biochemical Response Analysis

All biochemical response analyses will be performed using the PFS-FAS. PSA, ALP, and LDH values will be summarized descriptively as follows:

- Continuous variable summary statistics for baseline, each time point, and % change from baseline for each treatment arm
- Plots of the mean (\pm standard error) values over time for PSA, ALP, and LDH.
- Summary statistics of PSA doubling time with 95% CI for the mean PSA doubling time
- Summary statistics of maximum % change from baseline
- Categorical variable summary statistics and 95% CIs of PSA response ($\geq 50\%$ decrease and PSA $\geq 80\%$ decrease)
- Waterfall plot of the maximum % change from baseline in PSA for each patient
- Duration of PSA response ($\geq 50\%$ decrease) will be presented descriptively the same as DOR (Section 8.2.2).

Unscheduled labs will not be included in tables but will be provided in listings.

Treatment arm differences of % change from baseline in PSA, ALP, and LDH across all time points will be analyzed using mixed effects general linear models for repeated measures, under the assumption of Missing at Random (MAR). The fixed effects will include treatment arm, time (as a categorical variable), treatment by time interaction, and randomization stratification factors. An unstructured variance-covariance matrix for the repeated measures for a single patient will be used. In case of problems with fitting the model, as an alternative, a heterogeneous Toeplitz and AR(1) structures will be considered to reduce the number of parameters of the model. If necessary for the model fit, the outcome variables might be transformed. Details of any transformations used will be provided in the CSR. The differences in least square means between the treatment arms and corresponding 95% confidence interval at selected time points will be presented.

For PSA response, analyses will be the same as those described for binary outcome ORR (Section 8.2.2).

Duration of PSA response will be analyzed using a mixture distribution analysis, as described for DOR (Section 8.2.2).

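### Setting PSA doubling time to 0 when PSA is falling ranks responders as the fastest progressors in the descriptive summaries

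*SAP*

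**What the plan says.** SAP 8.1.3 computes post-baseline PSA doubling time as 0.693 divided by the sum of a common slope and a patient-specific slope from a random coefficient model of ln PSA on time. When the quotient is negative because PSA is flat or falling, the rule reads: "decreasing PSA levels as defined by a negative slope from the random coefficient linear model), the PSA doubling time is set to zero". SAP 5.6 has the same rule for baseline: "the PSA doubling time is set to 0".

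The zeros are then summarised as ordinary values:

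- SAP 8.2.3.2 plans "Summary statistics of PSA doubling time with 95% CI for the mean PSA doubling time", by arm, in the PFS-FAS.
- SAP 5 sets the general format: "Continuous data will be summarized using number of non-missing values (n), mean, standard deviation, median, minimum, and maximum values". A zero is non-missing.
- SAP 7.2 lists "Baseline PSA doubling time (months): continuous and categorical", with a cut at 6 months.

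In 8.1.3 the phrase "PSA doubling time will be missing" applies only when the baseline PSA is missing or below 0.2 ng/mL. Both definitions also require a minimum number of values of at least 0.2 ng/mL, spanning 8 weeks to 12 months. None of these conditions removes a patient for having a negative slope, and no section counts, separates or re-ranks the zeros.

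**The concern.** Doubling time runs from short (bad) to long (good), and a PSA that is not rising never doubles. Such a patient belongs beyond the long end of the scale, but the rule places him at the short end. PSA decline is the expected effect of the drug, so the rule works against whichever arm has more of it. The post-baseline table could show a lower mean or median doubling time on active because active lowers PSA more.

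The baseline table has the same fault. Inclusion criterion 11 (Protocol 4.1) accepts soft-tissue or bone progression without a PSA rise, so a man whose PSA is not rising at entry can be enrolled. He would be counted with those whose PSA doubles within 6 months.

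**Working it through.** **The rule itself.** ln 2 = 0.6931, which agrees with the SAP's 0.693. Applying doubling time = ln 2 / slope, with negatives replaced by 0:

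| PSA course | Raw (months) | Recorded | Baseline class |
|---|---|---|---|
| doubles in 1 month | 1.0 | 1.0 | ≤6 |
| doubles in 12 months | 12.0 | 12.0 | >6 |
| +1% per month | 69.7 | 69.7 | >6 |
| −1% per month | −69.0 | 0 | ≤6 |
| −50% per month | −1.0 | 0 | ≤6 |

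Every positive slope gives a value above 0, so each zero ranks below every patient with a rising PSA. This needs no assumption about the data.

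**Inputs for size.** The documents give no share of negative slopes. The nearest figures are in Protocol 1.1: a fall of at least 50% in 64% of patients in the phase 2 study of the drug, and results with a second hormonal agent "including PSA decline >50% in 4% to 22% of patients". These are falls, not fitted slopes. Smaller falls would raise the share; a fall followed by a rise would lower it. The illustrative range is 30% to 64% for active (s_A; the lower end is an assumption) and 4% to 22% for control (s_C). Arm sizes are 557 at 2:1, that is 371 and 186.

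**Mean.** SAP mean = (1 − share falling) × mean among risers. The zeros alone therefore multiply the active/control ratio of means by (1 − s_A)/(1 − s_C):

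| s_A | s_C = 4% | s_C = 22% |
|---|---|---|
| 64% | 0.36/0.96 = 0.375 | 0.36/0.78 = 0.46 |
| 50% | 0.50/0.96 = 0.52 | 0.50/0.78 = 0.64 |
| 30% | 0.70/0.96 = 0.73 | 0.70/0.78 = 0.90 |

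Active risers must double between 1/0.90 = 1.1 and 1/0.375 = 2.7 times as slowly as control risers before the SAP mean favours active.

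**Median.** With 371 active patients the median is the 186th ordered value, so it is exactly 0 when at least 186 slopes are negative. Binomial probability: 2.7% at a 45% share, 50% at 50%, 97.3% at 55%, above 99.9% at 64%.

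Below half, the outcome depends on the risers. Simulation used lognormal doubling times for risers (control median 4 months, log SD 0.8). The table gives the percentage of trials in which the active median falls below control; the range covers control shares of 22% and 4%.

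| s_A | Risers alike | Active risers 1.5× slower | Active risers 2× slower |
|---|---|---|---|
| 30% | 89 to 100 | 4 to 53 | 0 to 1 |
| 40% | >99 to 100 | 69 to 99 | 13 to 62 |
| 50% | 100 | >99 to 100 | 98 to >99 |

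At 64% the median reversed in every simulated trial.

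**Normal slopes instead of fixed shares.** With a control mean of 0.15 per month and active truly better in every row, the median reverses in these percentages of trials:

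| Active mean slope | SD 0.10 | SD 0.15 | SD 0.20 |
|---|---|---|---|
| 0.10 | 1 | 33 | 56 |
| 0.05 | 2 | 63 | 86 |
| 0 | 96 | >99 | >99 |
| −0.10 | 100 | 100 | 100 |

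At SD 0.05 to 0.075 there is no reversal for active means of 0.10 and 0.05, and 53% to 78% for a mean of 0. A separate simulation of the SAP's random coefficient model, in which patient slopes are shrunk, gave somewhat lower rates but the same pattern (39% to 61% at active mean 0.05 and SD 0.15).

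**Baseline class.** The ≤6-month proportion is inflated by exactly the share with a negative slope. With 10% negative and assumed lognormal risers (median 4 months, log SD 0.6), 77.6% are classed as ≤6 months, against 77.6 − 10 = 67.6% otherwise.

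**A separate weakness.** Slopes just above zero give very large values, so the mean of ln 2 / slope is unstable with or without the zeros. At SD 0.15 the 5th to 95th percentile of the control mean is about 5.5 to 32 months with zeros and 6.6 to 38 without. At active mean 0.10 the mean reverses in 30.4% of trials with zeros and 24.0% among risers only, so most of that comes from the reciprocal. At −0.10 the figures are 51.0% and 6.4%, so most comes from the zeros.

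**The case against.** The strongest reply is that little depends on this variable. Post-baseline doubling time is not a named endpoint, and SAP 8.2.3.2 also reports PSA response at 50% and 80%, a waterfall plot and percentage change over time, all of which show falling PSA in the right direction. The meaning of 0 is stated in the definition, and no positive slope can produce it. At baseline, randomisation balances the zeros in expectation. This stands, and it is why the point is minor. It does not make the doubling-time summary correct.

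The second reply is that the size is assumed. The 30% lower bound, the lognormal risers and the control slope of 0.15 have no source in the documents, and reversal runs from 0% to 100% across the scenarios. The simulations also ignore that patients may qualify for a doubling time at different rates by arm: early dropout was high in control, and some deep responders fall below 0.2 ng/mL. This too stands. The percentages show what can happen, not how likely it is. The direction of the error and the factor (1 − s_A)/(1 − s_C) do not depend on the simulation assumptions.

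A third reply is that the instability of the mean is a separate matter and a slope summary is a preference. The instability is indeed separate. It does bear on the choice of repair, because removing the zeros while keeping the mean would leave an unstable statistic.

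**Conclusion.** The concern holds, as a minor point. Followed exactly, the rule scores falling PSA as faster doubling than any rising PSA, and the zeros reach the by-arm mean, CI, median and minimum and the baseline class of 6 months or less. Reversal of the medians is certain when more than half of the active arm and under half of control have negative slopes; with fewer it may or may not occur. In the illustrative range the ratio of means is multiplied by 0.375 to 0.90. These sizes rest on assumed shares and slope distributions; the fault in direction does not.

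The reach is descriptive only. No test of doubling time is planned, and it is neither a stratification factor nor a subgroup. rPFS, OS, the key secondary endpoints, PSA response, percentage change and duration of PSA response are unaffected.

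**What to change.** In SAP 5.6 and 8.1.3, replace the assignment of zero with a category, not doubling (slope ≤ 0). This also covers a slope of exactly 0, where the quotient is undefined and the present condition (below zero) does not apply.

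In 8.2.3.2, report n and % not doubling by arm. Replace the mean doubling time and its CI with the mean ln PSA slope per month and its 95% CI. An acceptable alternative is the median doubling time with not doubling ranked longest, shown as not reached if it exceeds half.

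In 7.2, show not doubling as its own class or group it with more than 6 months, and replace the continuous baseline summary in the same way.

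Across the 20 normal-slope scenarios (five SDs by four active means), the mean slope put the arms in the wrong order in at most about 0.3% of trials. The worst case is SD 0.20 with 0.10 against 0.15: z = 0.05 / (0.20 × √(1/371 + 1/186)) = 2.78, or 0.27%. The re-ranked median did so in at most about 1.5%.

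The cost is SAP wording and programming; no new data are needed.
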